Appendix 2.9. Psoriatic Arthritis Disease Activity Score (PASDAS)

PASDAS (Helliwell et al 2013)⁶ is a composite PsA disease activity score that includes the following components: patient global joint and skin assessment (VAS in mm), physician global psoriatic arthritis assessment (VAS in mm), swollen (66 joints) and tender joint counts (68 joints), Leeds Enthesitis Index score, tender dactylitic digit score, physical component summary score (PCS) of SF-36v2 and CRP (mg/L).

$$\begin{aligned} \text{PASDAS} = & (((0.18 \times \sqrt{\text{Physician global VAS}}) + (0.159 \times \sqrt{\text{Patient global VAS}}) \\ & - (0.253 \times \sqrt{\text{SF36-PCS}}) + (0.101 \times \text{LN}(\text{Swollen joint count} + 1)) \\ & + (0.048 \times \text{LN}(\text{Tender joint count} + 1)) \\ & + (0.23 \times \text{LN}(\text{Leeds enthesitis index score} + 1)) \\ & + (0.37 \times \text{LN}(\text{Tender dactylitis count} + 1)) \\ & + (0.102 \times \text{LN}(\text{CRP} + 1)) + 2) \times 1.5 \end{aligned}$$

where LN() is the natural logarithm. For patient’s global joint and skin assessment (VAS), it is obtained only from the first question in the CRF for assessing subject’s global joint and skin, “In all the ways in which your PSORIASIS and ARTHRITIS, as a whole, affects you, how would you rate the way you felt over the past week?” The physician’s global psoriatic arthritis assessment (VAS) is obtained from the CRF at the prompt: “THE SUBJECT’S OVERALL PSORIATIC ARTHRITIS AT THIS TIME IS...”. The tender dactylitis digit score is the number of digits out of 20 (fingers and toes) where rating of either 2 (digit is tender and swollen (active)) or 3 (digit is very swollen and tender or very tender and swollen (highly active)) is registered. Any missing component will result in PASDAS as missing. The VAS data will need to be rescaled prior to any calculation (Section 6). A higher PASDAS score indicates a higher disease activity.

Appendix 2.10. Psoriasis Area and Severity Index (PASI)

The Psoriasis Area and Severity Index quantifies the severity of a subject’s psoriasis based on both *lesion severity* and the percentage of *body surface area* (BSA) affected.

- **Lesion severity:** The basic characteristics of psoriatic lesions – erythema, induration and scaling – provide a means for assessing the severity of lesions. Assessment of these three main signs is performed separately for four areas of the body: head, upper limbs, trunk, and lower limbs. Average erythema, induration and scaling are rated for each body area according to a 5-point scale: 0, no involvement; 1, slight; 2, moderate; 3, marked; 4, very marked.
- **Body surface area involvement (%BSA):** The extent (%) to which each of the four areas of the body is affected by psoriasis is assigned a numerical score according to the following area scoring criteria: 0, no involvement; 1, >0 to 9%; 2, 10 to 29%; 3, 30 to 49%; 4, 50 to 69%; 5, 70 to 89%; 6, 90 to 100%.

In each area, the sum of the severity rating scores for erythema, induration and scaling is multiplied by the score representing the percentage of this area involved by psoriasis,

multiplied by a weighting factor (head 0.1; upper limbs 0.2; trunk 0.3; lower limbs 0.4). The sum of the numbers obtained for each of the four body areas is the PASI.

$$\text{PASI} = 0.1A_h (E_h + I_h + S_h) + 0.2A_u (E_u + I_u + S_u) + 0.3A_t (E_t + I_t + S_t) + 0.4A_l (E_l + I_l + S_l)$$

Where A = area of involvement score; E = erythema; I = induration; S = scaling; h = head; u = upper limbs; t = trunk; l = lower limbs.

The PASI score can vary in increments of 0.1 units from 0.0 to 72.0, with higher scores representing increasing severity of psoriasis.

Each PASI clinical signs component score can be computed as:

$$\text{PASI}_E = 0.1A_h (E_h) + 0.2A_u (E_u) + 0.3A_t (E_t) + 0.4A_l (E_l)$$

$$\text{PASI}_I = 0.1A_h (I_h) + 0.2A_u (I_u) + 0.3A_t (I_t) + 0.4A_l (I_l)$$

$$\text{PASI}_S = 0.1A_h (S_h) + 0.2A_u (S_u) + 0.3A_t (S_t) + 0.4A_l (S_l)$$

Any missing component will result in PASI as missing.

BSA (number of handprints; %) will be an endpoint of interest.

Appendix 2.11. Physician Global Assessment (PGA) of Psoriasis (PGA-PsO)

The Physician Global Assessment of Psoriasis is scored on a 5-point scale, reflecting a global consideration of the erythema, induration and scaling across all psoriatic lesions. Average erythema, induration and scaling are rated separately over the whole body according to a 5-point severity scale, scored as 0 (none), 1, 2, 3, or 4 (most severe). The severity rating scores are summed and the average taken – the total average is rounded to the nearest whole number score to determine the PGA.

Appendix 2.12. Dermatology Life Quality Index (DLQI)

The DLQI is a general dermatology questionnaire that consists of 10 items that assess patient health-related quality of life (daily activities, personal relationships, symptoms and feelings, leisure, work and school, and treatment). The DLQI is scored such that a higher score indicates greater impairment.

Total raw score = sum (items 1, 2, 3, 4, 5, 6, 7, 8, 9, 10)

The scoring of each question other than Question 7 is:

Very much	is scored 3;
A lot	is scored 2;
A little	is scored 1;
Not at all	is scored 0;

Not relevant is scored 0.

For Question 7:

if yes, then scored 3;

if no or not relevant, then scored 0;

if it is answered “no” or “not relevant” but then either “a lot” or “a little” is checked this is then scored 2 or 1, respectively.

If a question is unanswered it is scored 0 and the scores are summed and expressed as usual out of a maximum of 30. If two or more questions are left unanswered the DLQI is not scored.

Appendix 2.13. Itch Severity Item (ISI)

The severity of itching due to psoriasis will be assessed using a single-item, 0 to 10 horizontal numeric rating scale (NRS). Subjects will be asked to assess their itch over the past 24 hours on the NRS anchored by the terms “no itching” (0) and “worst possible itching” (10) at the ends.

Appendix 2.14. Bath Ankylosing Spondylitis Disease Activity Index (BASDAI)

The BASDAI score is obtained by computing the mean score for the 2 questions related to morning stiffness (questions 5 and 6) and then adding that value to the sum of the scores for the first 4 questions and then dividing the total by 5. This can be written as:

$$\text{BASDAI} = (Q1 + Q2 + Q3 + Q4 + (Q5 + Q6)/2) / 5$$

The total score will range from 0.0 to 10.0 cm.

If the answer to either any 1 question is missing, then the BASDAI score will be calculated using the remaining non-missing answers. If >1 answers are missing, then the BASDAI is considered as missing (Ramiro, 2014).⁹

Explicitly, the calculation of BASDAI score for any 1 missing answer is detailed in the table below:

Missing Q5 or Q6	Missing any one of Q1-Q4	Formula
No	Yes	$\text{BASDAI} = [\text{sum of the 3 non-missing of } (Q1, Q2, Q3, Q4) + (Q5 + Q6)/2] / 4$
Yes	No	$\text{BASDAI} = [Q1 + Q2 + Q3 + Q4 + (\text{non-missing of } Q5 \text{ or } Q6)] / 5$

The raw VAS data will need to be rescaled to a 10 cm scale prior to any calculation ([Section 6](#)).

Appendix 2.15. EuroQol-5D Health Questionnaire 3-Level (EQ-5D-3L)

On the EQ-5D (subject version, 3 categories of response per question), 5 dimensions of health (mobility, self-care, usual activities, pain/discomfort and anxiety/depression) are assessed. The status of each dimension has three possible responses (no problem in the relevant health dimension to severe problems).

The EQ VAS records the patient's self-rated health on a vertical visual analogue scale where the endpoint is labelled 'Best imaginable health state' and 'Worst imaginable health state'. Based on the patient's mark on the VAS form a score ranging from 0 to 100 mm is recorded. The VAS data will need to be rescaled prior to any calculation ([Section 6](#)).

Appendix 2.16. Functional Assessment of Chronic Illness Therapy-Fatigue (FACIT-F)

FACIT-F is a 13 item questionnaire (each item score ranges from 0 to 4). There will be 3 endpoints derived: Δ FACIT-F total score, Δ FACIT-F experience domain score and Δ FACIT-F impact domain score. FACIT-F total score (range 0-52) is calculated by summing the 13 items. FACIT-F experience domain score (range 0-20) is calculated by summing 5 items of Q1 I feel fatigued, Q2 I feel weak all over, Q3 I feel listless ("washed out"), Q4 I feel tired and Q7 I have energy, while FACIT-F impact domain score (range 0-32) is calculated by summing the remaining 8 items. Note that all the scores except Q7 & Q8 should be reversed prior to summing for both the total score and the domain scores such that higher scores represent better functioning.

All responses are added with equal weight to obtain the total score. In cases where some answers are missing, a total score is prorated from the score of the answered items, so long as more than 50% of the items (ie, at least 7 of 13 for FACIT-F total score, at least 3 of 5 for FACIT-F experience domain score, and at least 5 of 8 for FACIT-F impact domain score) are answered.

Appendix 2.17. Short Form 36 (SF-36, version 2, acute)

The SF-36 v.2 (Acute version) is a 36-item generic health status measure. It measures 8 general health concepts or domains: physical functioning, role physical, bodily pain, general health, vitality, social functioning, role emotional and mental health. These domains can also be summarized as physical and mental component scores.

These 8 domains are as follows:

- a. Physical Functioning (PF). This score is based on the responses to the 10 items that compose Question 3 and reflects the degree to which various physical activities have been limited in the previous week by the subject's health.

- b. Role-Physical (RP). This score is based on the responses to the four items that compose Question 4 and reflects the relative amount of time that the subject has had problems with work or other regular daily activities as a result of their physical health during the previous week.
- c. Bodily Pain (BP). This score is based on the responses to Questions 7 and 8 and reflects bodily pain and its effects on normal work during the previous week.
- d. General Health (GH). This score is based on responses to Question 1 and the four items in Question 11 and reflects the subject's perception of their general health during the previous week.
- e. Vitality (VT). This score is based on responses to Question 9 items a, e and g, and reflects the subject's physical energy level relative to time during the previous week.
- f. Social Functioning (SF). This score is based on responses to Questions 6 and reflects how physical health or emotional problems have interfered with social activities during the previous week.
- g. Role-Emotional (RE). This score is based on responses to the three items in Question 5 and reflects the amount of time during the previous week that emotional problems have interfered with work or regular daily activities.
- h. Mental Health (MH). This score is based on responses to Question 9 items b, c, d, f, and h and reflects various mental/emotional states relative to time during the previous week.
- i. Health Transition (TR). This score is based on the response to Question 2 and is a rating of current general health compared to one week previous.

The summary component scores are:

- Physical Component Summary (PCS).
- Mental Component Summary (MCS).

The summary component scores, PCS and MCS, are based on a normalized sum of the 8 scale scores PF, RP, BP, GH, VT, SF, RE, and MH. All domains and summary components are scored such that a higher score indicates a higher functioning or health level.

Data Derivation Details to Obtain Scale Scores for SF-36v2

VARIABLE	DERIVATION
SF-36v2 PF scale score	
raw score = sum (items 3A, 3B, 3C, 3D, 3E, 3F, 3G, 3H, 3I, 3J)
 
$PF = (\text{raw score} - 10) * 5$
 
$PF_Z = (PF - 82.62455) / 24.43176$
 
PF scale score = (PF_Z*10) + 50
 
When calculating the raw score, if 5 or more of the items are non-missing then replace any missing values as follows:
 
Calculate the mean of the answered questions, using the number of answered questions as the denominator. Substitute the mean for any missing scores.
 
Otherwise, if less than 5 of the items are non-missing then PF scale score is missing.
 
The response scale for each activity ranges from 1 to 3 where 1=limited a lot, 2=limited a little, and 3=not limited at all.
 
A higher PF scale score indicates better physical functioning.

SF-36v2 RP scale score	
raw score = sum (items 4A, 4B, 4C, and 4D)
 
$RP = [(\text{raw score} - 4) / 16] * 100$
 
$RP_Z = (RP - 82.65109) / 26.19282$
 
RP scale score = (RP_Z * 10) + 50
 
When calculating the raw score, if 2 or more of the items are non-missing then replace any missing values as follows:
 
Calculate the mean of the answered questions, using the number of answered questions as the denominator. Substitute the mean for any missing scores.
 
Otherwise, if less than 2 of the items are non-missing then RP scale score is missing.
 
The response scale for each item ranges from 1 to 5 where 1=All of the time, 2=Most of the time, 3=Some of the time, 4=A little of the time, and 5=None of the time. A higher RP scale score indicates better role-physical functioning.

SF-36v2 BP scale score	
raw score = sum (reversed item 7 and reversed item 8) $BP = (raw\ score - 2) * 10$ $BP_Z = (BP - 73.86999) / 24.00884$ BP scale score = (BP_Z * 10) + 50
 
Reverse direction of Item 7 as follows: if=1, set to 6; if=2, set to 5.4; if=3, set to 4.2; if=4, set to 3.1; if=5, set to 2.2; if=6, set to 1.
 
Reverse direction of item 8 as follows: if=1 and original value of item 7=1, set to 6; if=1 and original value of item 7>=2, set to 5; if=2, set to 4; if=3, set to 3; if=4, set to 2; if=5, set to 1.
 
If item 7 is answered and item 8 is missing, set reversed 8 = reversed 7 as defined above. If 8 is answered and 7 is missing, set reversed 7 as reverse item 8 as follows: if=1, set to 6; if=2, set to 4.75; if=3, set to 3.5; if=4, set to 2.25; if=5, set to 1.
 
If 1 or more questions were answered, calculate BP scale score as defined above. If neither question was answered then BP scale score is missing.
 
The scale for Question 7, amount of bodily pain, ranges from 1 to 6 where 1=None, 2=Very mild, 3=mild, 4=Moderate, 5=Severe, and 6=Very severe. The scale for Question 8, the degree to which pain interfered with normal work, ranges from 1 to 5 where 1=Not at all, 2=A little bit, 3=Moderately, 4=Quite a bit, and 5=Extremely. A higher BP scale score indicates lack of bodily pain.

------------------------	---

SF-36v2 GH scale score	
raw score = sum (reversed item 1, item 11A, reversed 11B, 11C and reversed 11D) GH = (raw score -5) * 5 $GH_Z = (GH - 70.78372) / 21.28902$ GH scale score = (GH_Z * 10) + 50
 
Reverse direction of Item 1 as follows: if=1, set to 5; if=2, set to 4.4; if=3, set to 3.4; if=4, set to 2; if=5, set to 1.
 
Reverse direction of item 11B and 11D by subtracting score from 6.
 
When calculating the raw score, if 3 or more of the items are non-missing then replace any missing values as follows:
 
Calculate the mean of the answered questions, using the number of answered questions as the denominator. Substitute the mean for any missing scores.
 
Otherwise, if less than 3 of the items are non-missing then GH scale score is missing.
 
Responses for Question 1, an assessment of self-perceived health status, range from 1 to 5 where 1=Excellent, 2=Very good, 3=Good, 4=Fair, and 5=Poor. Responses for the items in Question 11 range from 1 to 5 where 1=Definitely true, 2=Mostly true, 3=Don't know, 4=Mostly false, and 5=Definitely false and reflect the subject's perception of their relative health and expectations of their future health status. A higher GH scale score indicates better general health perceptions.

SF-36v2 VT scale score	
raw score = sum (reversed item 9a, reversed 9e, 9g and 9i) $VT = [(raw\ score - 4) / 16] * 100$ $VT_Z = (VT - 58.41968) / 20.87823$ VT scale score = (VT_Z * 10) + 50
 
Reverse direction of Items 9a and 9e by subtracting score from 6.
 
When calculating the raw score, if 2 or more of the items are non-missing then replace any missing values as follows:
 
Calculate the mean of the answered questions, using the number of answered questions as the denominator. Substitute the mean for any missing scores.
 
Otherwise, if less than 2 of the items are non-missing then VT scale score is missing.
 
The scale for these items ranges from 1 to 5 where 1=All of the time, 2=Most of the time, 3=Some of the time, 4=A little of the time, and 5=None of the time. A higher VT scale score indicates more vitality.


SF-36v2 SF scale score
	
raw score = sum (reversed 6 and 10) $SF = [(raw\ score - 2) / 8] * 100$ $SF_Z = (SF - 85.11568) / 23.24464$ SF scale score = (SF_Z * 10) + 50
 
Reverse direction of score for item 6 by subtracting score from 6.
 
When calculating the raw score, if 1 of the items is missing then substitute the missing score with the score on the non- missing item. If both items are missing then SF scale score is missing.
 
Responses to Question 6, an assessment of the extent to which health/emotional problems interfered with social activities, range from 1 to 5 where 1=Not at all, 2=Slightly, 3=Moderately, 4=Quite a bit, and 5=Extremely. Responses to Question 10 reflect the amount of time that health/emotional problems interfered with social activities and range from 1 to 5 where 1=All of the time, 2=Most of the time, 3=Some of the time, 4=A little of the time, and 5=None of the time. A higher SF scale score indicates better social functioning.

SF-36v2 RE scale score
	
raw score = sum (items 5A, 5B, and 5C) $RE = [(raw\ score - 3) / 12] * 100$ $RE_Z = (RE - 87.50009) / 22.01216$ RE scale score = (RE_Z * 10) + 50
 
When calculating the raw score, if 2 or more of the items are non-missing then replace any missing values as follows:
 
Calculate the mean of the answered questions, using the number of answered questions as the denominator. Substitute the mean for any missing scores.
 
Otherwise, if less than 2 of the items are non-missing then RE scale score is missing.
 
Responses to the items in Question 5 range from 1 to 5 where 1=All of the time, 2=Most of the time, 3=Some of the time, 4=A little of the time, and 5=None of the time. A higher RE scale score indicates better role-emotional functioning.


SF-36v2 MH scale score
	
raw score = sum (items 9B, 9C, reversed 9D, 9F and reversed 9H) $MH = (raw\ score - 5) * 5$ $MH_Z = (MH - 75.76034) / 18.04746$ MH scale score = (MH_Z * 10) + 50
 
Reverse direction of scores for 9D and 9H, by subtracting score from 6.
 
If 3 or more of the items are non-missing then replace any missing values as follows:
 
Calculate the mean of the answered questions, using the number of answered questions as the denominator. Substitute the mean for any missing scores.
 
Otherwise, if less than 3 of the items are non-missing then MH scale score is missing.
 
The scale for these items ranges from 1 to 5 where 1=All of the time, 2=Most of the time, 3=Some of the time, 4=A little of the time, and 5=None of the time. A higher MH scale score indicates better mental health.

SF-36v2 TR scale score	
raw score = item 2 TR scale score = raw score
 
The scale for this item ranges from 1 to 5 where 1=Much better now than one week ago, 2=Somewhat better now than one week ago, 3=About the same as one week ago, 4=Somewhat worse now than one week ago, and 5=Much worse now than one week ago. A higher TR scale score indicates worse general health currently relative to one week previous.

SF-36v2 PCS score	
PCS score includes the 8 scales for GH, PF, RP, RE, SF, MH, BP, and VT.
 
PF1= (PF-82.62455)/24.43176; RP1=(RP-82.65109)/26.19282; BP1=(BP-73.86999)/24.00884; GH1 = (GH-70.78372)/21.28902; VT1= (VT-58.41968)/20.87823; SF1=(SF-85.11568)/23.24464; RE1= (RE-87.50009)/22.01216; MH1=(MH-75.76034)/18.04746;
 
Raw Score = ((GH1*.24954)+(PF1* .42402)+(RP1*.35119)+ (RE1*-.19206)+(SF1*-.00753)+(MH1*-.22069)+(BP1*.31754)+ (VT1*.02877))
 
PCS Summary Scale Score = (raw score *10) + 50
 
Raw Score is missing if one of the component scale scores is missing.

SF-36v2 MCS score	
MCS score includes the 8 scales for GH, PF, RP, RE, SF, MH, BP, and VT.
 
PF1= (PF-82.62455)/24.43176; RP1=(RP-82.65109)/26.19282; BP1=(BP-73.86999)/24.00884; GH1 = (GH-70.78372)/21.28902; VT1= (VT-58.41968)/20.87823; SF1=(SF-85.11568)/23.24464; RE1= (RE-87.50009)/22.01216; MH1=(MH-75.76034)/18.04746;
 
Raw Score =((GH1*-.01571)+(PF1*-.22999)+(RP1*-.12329)+ (RE1*.43407)+(SF1*.26876)+(MH1*.48581)+(BP1*-.09731)+ (VT1*.23534))
 
MCS Summary Concept Score = (raw score *10) + 50
 
Raw Score is missing if one of the component scale scores is missing.

Appendix 3. Criteria for Clinical Diagnosis of the Metabolic Syndrome

Criteria for clinical diagnosis of the metabolic syndrome will be based on the 2009 Joint Statement Harmonizing the Metabolic Syndrome (Alberti et al, 2009).¹ There are 5 measures or risk factors as detailed in Table 1 of the 2009 Joint statement and excerpted below:

Measure	Categorical Cut Points
Elevated waist circumference*	Population- and country-specific definitions
Elevated triglycerides (drug treatment for elevated triglycerides is an alternate indicator†)	≥150 mg/dL (1.7 mmol/L)
Reduced HDL-C (drug treatment for reduced HDL-C is an alternate indicator†)	<40 mg/dL (1.0 mmol/L) in males; <50 mg/dL (1.3 mmol/L) in females
Elevated blood pressure (antihypertensive drug treatment in a patient with a history of hypertension is an alternate indicator)	Systolic ≥130 and/or diastolic ≥85 mm Hg
Elevated fasting glucose‡ (drug treatment of elevated glucose is an alternate indicator)	≥100 mg/dL

HDL-C indicates high-density lipoprotein cholesterol.

*It is recommended that the IDF cut points be used for non-Europeans and either the IDF or AHA/NHLBI cut points used for people of European origin until more data are available.

†The most commonly used drugs for elevated triglycerides and reduced HDL-C are fibrates and nicotinic acid. A patient taking 1 of these drugs can be presumed to have high triglycerides and low HDL-C. High-dose ω-3 fatty acids presumes high triglycerides.

‡Most patients with type 2 diabetes mellitus will have the metabolic syndrome by the proposed criteria.

Any 3 abnormal findings out of the 5 measures will qualify a subject for the metabolic syndrome.

The baseline data of qualifying study will be used to derive the metabolic syndrome.

- Any drug treatment taken on Day 0 recorded on the “CONCOMITANT DRUG TREATMENT - ANTI-DIABETIC” CRF will be considered having the drug treatment of elevated glucose criterion satisfied.
- Any drug treatment taken on Day 0 recorded on the “CONCOMITANT DRUG TREATMENT - ANTI-HYPERTENSIVE MEDICATIONS” CRF will be considered having the drug treatment of elevated blood pressure criterion satisfied.

- Any drug treatment taken on Day 0 recorded on the “CONCOMITANT DRUG TREATMENT – LIPID LOWERING AGENTS” CRF will be considered having the drug treatment of elevated triglycerides criterion satisfied.
- For the HDL-C criterion, only the lab categorical cut points will be considered and the drug treatment will not be considered.
- The waist circumference thresholds will be population and country specific per Table 2 of the 2009 Joint Statement excerpted below. Explicitly, the US specific threshold will be used for the subjects enrolled from US, the Canada threshold for the subjects enrolled from Canada, the European threshold for the subjects enrolled from Western Europe, Eastern Europe and Russia, the Asian (including Japanese) threshold for the subjects enrolled from Asia, and Ethnic Central and South American threshold for the subjects enrolled from Central and South America.

Population	Organization (Reference)	Recommended Waist Circumference Threshold for Abdominal Obesity	
		Men	Women
Europid	IDF (4)	≥94 cm	≥80 cm
Caucasian	WHO (7)	≥94 cm (increased risk) ≥102 cm (still higher risk)	≥80 cm (increased risk) ≥88 cm (still higher risk)
United States	AHA/NHLBI (ATP III)* (5)	≥102 cm	≥88 cm
Canada	Health Canada (8,9)	≥102 cm	≥88 cm
European	European Cardiovascular Societies (10)	≥102 cm	≥88 cm
Asian (including Japanese)	IDF (4)	≥90 cm	≥80 cm
Asian	WHO (11)	≥90 cm	≥80 cm
Japanese	Japanese Obesity Society (12)	≥85 cm	≥90 cm
China	Cooperative Task Force (13)	≥85 cm	≥80 cm
Middle East, Mediterranean	IDF (4)	≥94 cm	≥80 cm
Sub-Saharan African	IDF (4)	≥94 cm	≥80 cm
Ethnic Central and South American	IDF (4)	≥90 cm	≥80 cm

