- Baseline enthesitis index measured by SPARCC enthesitis index (continuous) for those subjects with SPARCC enthesitis index >0 at baseline;
- Baseline enthesitis index measured by LEI (continuous) for those with LEI >0 at baseline;
- Baseline presence of dactylitis (yes, no). Yes is defined for those subjects with baseline DSS >0 ;
- Baseline DSS (continuous) for those subjects with DSS >0 at baseline;
- Baseline presence of spondylitis (yes, no). Yes is defined for those subjects with presence of spondylitis at screening and baseline BASDAI >0 ;
- Baseline BASDAI (0, >0 to <4 , ≥ 4) for those subjects with presence of spondylitis at screening. BASDAI score ≥ 4 indicates active disease/suboptimal treatment;
- Baseline BASDAI (continuous) for those subjects with presence of spondylitis at screening and BASDAI >0 at baseline;
- Baseline total psoriatic BSA (0, >0 to <3 , $\geq 3\%$);
- Baseline total psoriatic BSA (continuous) for those with BSA $>0\%$ at baseline;
- Baseline PASI (0, >0 to ≤ 20 , >20);
- Baseline PASI (continuous) for those subjects with BSA $\geq 3\%$ and PASI >0 at baseline;
- Baseline PGA-PsO (0, 1, 2, 3, 4);
- Baseline PGA-PsO (continuous) for those subjects with PGA-PsO >0 at baseline;
- Number (%) of subjects with baseline PGA-PsO ≥ 3 , PASI ≥ 12 and BSA $\geq 10\%$;
- Baseline SF-36v2 (8 domains, physical component score [PCS] and mental component score [MCS]);

- Baseline FACIT-F (FACIT-F total score, FACIT-F experience score and FACIT-F impact score);
- Baseline DLQI (<5 , ≥ 5 ; and continuous);
- Baseline CRP (≤ 2.87 , > 2.87 mg/L; and continuous);
- Baseline diabetes mellitus (yes, no) (see [Appendix 4](#) for definition);
- Baseline metabolic syndrome (yes, no) (see [Appendix 3](#) for definition);
- Baseline cardiovascular risks per PDS and detailed in the statistical programming plan;
- Baseline rheumatoid factor positive (yes, no);
- Baseline cyclic citrullinated peptide antibody positive (yes, no).

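### SAP Appendix 3 does not implement the metabolic-syndrome definition it excerpts: its two lipid drug rules misclassify subjects, in opposite directions

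*SAP*

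**What the plan says.** SAP Appendix 3 bases baseline metabolic syndrome on a published joint statement and reproduces its table of five measures: waist, triglycerides, HDL-C, blood pressure and glucose. The threshold is plain: "Any 3 abnormal findings out of the 5 measures will qualify a subject for the metabolic syndrome".

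The triglyceride row reads "Elevated triglycerides (drug treatment for elevated triglycerides is an alternate indicator", with a laboratory cut point of 150 mg/dL. The footnote to the two lipid rows says "The most commonly used drugs for elevated triglycerides and reduced HDL-C are fibrates and nicotinic acid", and continues: "A patient taking 1 of these drugs can be presumed to have high triglycerides and low HDL-C". High-dose omega-3 fatty acids are added for triglycerides only.

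The SAP's operational bullets follow. A Day 0 entry on the lipid-lowering-agents page is enough for triglycerides: the "CRF will be considered having the drug treatment of elevated triglycerides criterion satisfied". There is no filter by drug class or indication. The next bullet reads "For the HDL-C criterion, only the lab categorical cut points will be considered and the drug treatment will not be considered".

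The variable is a yes/no row in the LTE baseline summaries (SAP Section 8.3.1). It is also listed among the sub-study baseline characteristics (SAP Appendix 6, Section 7.3.1).

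**The concern.** Appendix 3 applies one footnote too widely to one lipid measure and not at all to the other. A subject who takes a drug only to lower LDL cholesterol, with triglycerides below 150 mg/dL, is credited with a criterion that the excerpt does not give. A subject on a fibrate or nicotinic acid, whom the excerpt presumes to meet both lipid measures, is credited with one unless the HDL-C value is itself below the cut point. Appendix 3 gives no reason for either departure.

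Readers of the baseline table will assume that the cited definition was applied. The reported prevalence will not be the one that definition gives, and individual subjects will be misclassified in both directions even where the errors cancel in the total.

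**Working it through.** The documents state no prevalence or drug use for this variable, so there is no figure to reproduce. The rules can be compared exactly, and the size can only be illustrated.

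**Inputs from SAP Appendix 3.** Let W, T, H, B and G be 1 if the clinical or laboratory finding is present for waist, triglycerides, HDL-C, blood pressure and glucose, and 0 otherwise. That gives 2^5 = 32 patterns. The syndrome is present when the count is at least 3.

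| Lipid drug on Day 0 | Count under the excerpt | Count under the SAP rules |
|---|---|---|
| None | W+T+H+B+G | W+T+H+B+G |
| LDL-lowering only | W+T+H+B+G | W+1+H+B+G |
| Fibrate or nicotinic acid | W+1+1+B+G | W+1+H+B+G |

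**Exact comparison.**

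- No lipid drug: no pattern differs.
- LDL-lowering only: the counts differ only when T = 0, and the threshold is crossed only when exactly two of W, H, B and G are present. That is C(4,2) = 6 patterns, all falsely positive.
- Fibrate or nicotinic acid: the counts differ only when H = 0, and the threshold is crossed only when exactly one of W, B and G is present. That is 3 choices × 2 values of T = 6 patterns, all falsely negative.

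If only the triglyceride rule is corrected, the 6 falsely positive patterns change to no and none changes to yes. That rule taken alone can therefore only raise prevalence. The HDL-C rule works the other way. The counts are of patterns, not of subjects.

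**Illustrative size.** Component prevalences, independence between components, lipid-drug use u and the fibrate/nicotinic acid share f among users are all assumptions.

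- False positives per LDL-only user: a = (1 − pT) × P(exactly two of W, H, B, G)
- False negatives per fibrate/nicotinic acid user: b = (1 − pH) × P(exactly one of W, B, G)
- Net error in prevalence: u × [(1 − f)a − f·b], which is zero at f = a/(a + b)

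| Assumed prevalences (W, T, H, B, G) | a | b | Zero at f |
|---|---|---|---|
| 0.40, 0.25, 0.25, 0.40, 0.25 | 0.219 | 0.337 | 0.394 |
| 0.55, 0.35, 0.35, 0.55, 0.40 | 0.246 | 0.246 | 0.501 |
| 0.70, 0.50, 0.50, 0.70, 0.55 | 0.172 | 0.119 | 0.591 |

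For the middle row, P(exactly one of W, B, G) = 0.55×0.45×0.60 + 0.55×0.45×0.60 + 0.45×0.45×0.40 = 0.378, so b = 0.65 × 0.378 = 0.246.

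If every user takes an LDL-lowering drug (f = 0), the net error runs from 0.10 × 0.172 = +1.7 points to 0.30 × 0.246 = +7.4 points. In the middle row at 20% use it is +1.97 points at f = 0.3, about zero at f = 0.5, and −1.96 points at f = 0.7.

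**The case against.** The strongest reply is that this is an openly stated operational definition. Appendix 3 says its criteria are based on the joint statement, and its drug bullets share one convention: presence on a CRF page stands for treatment. The blood-pressure bullet does the same and drops the excerpt's condition of a history of hypertension. This explains where the triglyceride rule came from. It does not justify a rule that contradicts the excerpted criterion, and it does not explain why the convention is abandoned for HDL-C.

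Four further objections stand:

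- The CRF page is not shown. That it captures LDL-lowering drugs is a fair inference from its title, not a documented fact.
- The footnote names the most commonly used drugs, which is not an exclusive list. A closed class list would be a new departure from the excerpt.
- The variable is descriptive. The LTE has no statistical models (SAP Section 6.4), and the covariate in the sub-study model is the endpoint's own baseline value (SAP Appendix 6, Section 5.4). The same rule applies to both sub-study arms.
- Nothing in the documents says that this row supports interpretation of the lipid or cardiovascular results. Baseline cardiovascular risks are summarized separately in SAP Section 8.3.1.

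A reader might infer from the triglyceride rule that baseline metabolic syndrome is overstated. The documents do not support that without a condition, because the HDL-C rule understates it in fibrate and nicotinic acid users and the mix of lipid drugs is not given.

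**Conclusion.** The departure from the excerpted definition is established from Appendix 3 alone, as are the 6 false-positive and 6 false-negative patterns. The direction and size of the net error in prevalence are not. Net overstatement is likely if most lipid-lowering drugs in these subjects are LDL-lowering, but that is a supposition about the drug mix. The range of about +1.7 to +7.4 points applies only if no user takes a fibrate or nicotinic acid. The break-even share of about 39-59% rests on the same assumed, independent prevalences. Correlation between the components would change these sizes but not the pattern counts.

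This is a minor point. It concerns one baseline characteristic in the LTE and the sub-study, and no endpoint, model or sample size changes. It is worth correcting because the reported row would otherwise not be what its citation says it is.

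**What to change.** In SAP Appendix 3, make two changes:

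1. Restrict the triglyceride drug indicator to coded drugs for elevated triglycerides (for example fibrates, nicotinic acid and high-dose omega-3 fatty acids), so that a drug given only to lower LDL cholesterol does not count.
2. Apply the fibrate/nicotinic acid indicator to the HDL-C criterion, as the footnote does.

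If the sponsor prefers the present rules, Appendix 3 and the table footnote should state both as deliberate departures, with the reason.

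The cost is a change of wording, a drug-class filter and a dose rule for omega-3. SAP Section 8.2.3 already has medications tabulated with the WHO-Drug dictionary. The Day 0 entries come from the qualifying studies, so the sponsor should confirm that they are coded in the same way and whether omega-3 is recorded on this page. No new data collection is needed.
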